2 SCHEDULE OF EVALUATIONS

Table 2 Schedule of Evaluations

Procedures	Visit 1	Visit 2
	24-27 Months	30-33 Months
	24-Month Study Visit	30-Month Study Visit / End of Study
Inclusion/Exclusion Criteria	X	
ICF/HIPAA	X	
Record AEs	X	X
Prior and Concomitant Medications	X	X
IDEEL	X	X
EQ-5D-5L	X	X
BCDVA	X	X
External Ocular Examination	X	X
Slit-Lamp Examination	X	X
Corneal Photography Without Fluorescein	X	X
Instillation of Fluorescein	X	X
TFBUT	X	X
Corneal Photography with Fluorescein	X	X
Corneal Sensitivity Testing	X	X
Schirmer Test (w/o Anesthesia)	X	X
CCI		
CCI		

3 BACKGROUND INFORMATION

The DEFENDO Study was aimed at evaluating the efficacy and safety of OXERVATE™ 0.002% (20 mcg/mL) cenegermin-bkbbj ophthalmic solution administered 6 times daily for 8 weeks in patients with Stage 1 neurotrophic keratitis (NK).

The current study is a long-term study evaluating the clinical outcomes of patients at 24 months and 30 months after completion of the DEFENDO Study.

NK, also known as neurotrophic keratopathy/keratitis, is a rare degenerative corneal disease caused by an impairment of corneal nerve innervation leading to a decrease or absence in corneal sensation. The cornea is an avascular tissue that is provided with the richest innervation of all body tissues via the trigeminal nerve. Corneal hypoesthesia or anesthesia and decreased reflex tearing resulting from impaired corneal innervation can lead to a corneal epitheliopathy with a subsequent breakdown of the corneal epithelium, leading to potential visual impairment. Abnormal corneal sensation and epithelial defects with a poor tendency for spontaneous healing are the primary clinical manifestations of NK, which increase the risk for corneal complications associated with vision loss such as a persistent epithelial defect (PED), ulceration, melting, perforation, and infectious keratitis. NK has been divided into three stages according to the Mackie classification scheme ([Appendix 4](#)) and treatment recommendations are based on the severity of corneal involvement. ^[1]

Based on the Mackie scale, Stage 1 NK is defined by the presence of an epithelial dystrophy or punctate keratopathy accompanied by corneal hypoesthesia. Stage 1 NK requires discontinuation of all topical medications and the administration of preservative-free artificial tears (PF-AT). While some Stage 1 NK patients may heal, many cases progress to Stage 2 NK. Based on the Mackie scale, Stage 2 NK is defined by the presence of a PED. The goal of Stage 2 treatment is to avoid progression of the disease to a corneal ulcer. The same therapeutic approaches as in Stage 1 are used in patients with Stage 2 often accompanied by the addition of patching or therapeutic contact lenses and the use of prophylactic antibiotics to prevent the risk of corneal infection. Based on the Mackie scale, Stage 3 NK is defined by the presence of a corneal ulcer, which may progress to corneal melting and perforation. When a corneal ulcer develops, therapy is aimed at promoting corneal healing and preventing corneal melting or perforation. Surgical procedures at this stage (tarsorrhaphy, flap procedures, and amniotic membrane transplantation) can preserve or restore ocular integrity but at the expense of cosmetic appearance and visual function. ^[2, 3] As of today, the only Food and Drug Administration (FDA) approved pharmacologic therapy for the treatment of NK is

OXERVATE™ 0.002% (20 mcg/mL) cenegeamin-bk bj ophthalmic solution, a recombinant human nerve growth factor (rhNGF).^[4, 5]

Nerve growth factor (NGF) is a polypeptide essential for the survival and growth of sympathetic and sensory neurons, and for differentiation of neurons in the central nervous system. It binds with at least two classes of receptors: high-affinity tropomyosin receptor kinase A (TrkA), a transmembrane tyrosine kinase, and Low-Affinity Nerve Growth Factor Receptor (LNGFR), also known as p75 neurotrophin receptor (p75NTR).^[6, 7]

NGF and its receptors TrkA and p75 are expressed in the anterior segment of the eye (iris, ciliary body, lens, cornea, and conjunctiva), and NGF is released in the aqueous humor. Several pieces of experimental evidence suggest that NGF affects all tissues of the anterior ocular segments, playing a crucial role in the physiopathology of several anterior ocular segment diseases.^[8, 9]

OXERVATE™ 0.002% (20 mcg/mL) cenegeamin-bk bj ophthalmic solution is a rhNGF approved by the FDA in August 2018, and it is indicated for the treatment of NK. Relevant pre-clinical, toxicological, and clinical data are summarized below and can be found in the Package Insert ([Appendix 3](#)).^[4]

3.1 RELEVANT NON-CLINICAL PHARMACOLOGY

Both in vitro and in vivo data illustrate the biological activity of NGF in terms of neuronal growth and differentiation, as well as in prevention of apoptosis of retinal ganglion cells. Cultured corneal/limbal cells of rabbit respond well to the proliferation stimulus induced by adding rhNGF or Murine Nerve Growth Factor (mNGF) to their culture media.^[10-12]

OXERVATE™ 0.002% (20 mcg/mL) cenegeamin-bk bj ophthalmic solution, a rhNGF, is the first FDA-approved pharmacologic treatment that targets the root pathogenesis of NK.^[4]

Cenegeamin-bk bj, the active ingredient of OXERVATE™ 0.002% (20 mcg/mL) cenegeamin-bk bj ophthalmic solution, is structurally identical to the human nerve growth factor (NGF) protein made in ocular tissues.

NGF is an endogenous protein involved in the differentiation and maintenance of neurons, which acts through specific high-affinity (i.e., TrkA) and low-affinity (i.e., p75NTR) nerve growth factor receptors in the anterior segment of the eye to support corneal innervation and integrity. Endogenous NGF is believed to support corneal integrity through 3 mechanisms: corneal innervation, cell proliferation, and tear secretion (shown in preclinical models).^[1, 2, 8, 13]

3.2 A SUMMARY OF CLINICAL DATA

The safety, efficacy, and FDA approval of OXERVATE™ 0.002% (20 mcg/mL) cenegermin-bk bj ophthalmic solution, was based upon a total of 151 patients with NK who completed one of two, eight-week, randomized controlled multi-center, double-masked studies. In the first study conducted in Europe, CCI [REDACTED] patients were randomized into three different groups. One group received OXERVATE™ 0.002% (20 mcg/mL) cenegermin-bk bj ophthalmic solution, a second group received 10 mcg/mL cenegermin, and the third group received vehicle.^[14] In the second study conducted in the US, CCI [REDACTED] patients were randomized into two groups. One group was treated with OXERVATE™ 0.002% (20 mcg/mL) cenegermin-bk bj ophthalmic solution, and the other group was treated with vehicle.^[15] All eye drops in both studies were given six times daily at 2-hour intervals in the affected eye(s) for eight weeks. In the first study, only patients with the disease in one eye were enrolled, while in the second study, patients with the disease in both eyes were treated in both eyes (bilaterally), the worse eye was considered the study eye for efficacy evaluations. Complete corneal healing (defined as absence of staining of the corneal lesion and no persistent staining in the rest of the cornea at eight weeks) was demonstrated in 72 percent of patients treated with OXERVATE™ 0.002% (20 mcg/mL) cenegermin-bk bj ophthalmic solution compared to 33.3 percent of patients ($p<0.001$) treated with vehicle in the REPARO trial. For the US trial, CCI [REDACTED] 65.2 percent of patients treated with OXERVATE™ 0.002% (20 mcg/mL) cenegermin-bk bj ophthalmic solution compared to 16.7 percent of patients treated with vehicle had complete corneal healing at week-8.^[14, 15]

The data from these two studies were enclosed into the biologics license application (BLA), and the FDA granted the approval for OXERVATE™ 0.002% (20 mcg/mL) cenegermin-bk bj ophthalmic solution for the treatment of all stages of NK.^[4]

The phase IV DEFENDO Study involving OXERVATE™ 0.002% (20 mcg/mL) cenegermin-bk bj ophthalmic solution has since been undertaken to provide additional efficacy and safety information related to OXERVATE™ 0.002% (20 mcg/mL) cenegermin-bk bj ophthalmic solution. This study enrolled 37 Stage 1 NK patients who were treated with OXERVATE™ 0.002% (20 mcg/mL) cenegermin-bk bj ophthalmic solution 6 times per day at 2-hour intervals for eight weeks. The DEFENDO Study reported 33 probable and 20 possible adverse events (AEs) that were determined to be related to the Study Product; however, only 3 patients discontinued the study because of the AEs they experienced. While these data are still being analyzed, the DEFENDO Long-Term Follow-up Study is a continuation of the DEFENDO Study, which aims to understanding the efficacy and safety OXERVATE™.

0.002% (20 mcg/mL) cenegeamin-bk bj ophthalmic solution at 24 and 30 months after the completion of the DEFENDO Study.

3.3 STUDY RATIONALE

This clinical study has been designed as a long-term follow-up study to the DEFENDO Study to understand the long-term clinical outcomes of OXERVATE™ 0.002% (20 mcg/mL) cenegeamin-bk bj ophthalmic solution in a group of Stage 1 NK patients who complete the DEFENDO Study. The primary objectives are to evaluate the long-term safety and efficacy (healing) of OXERVATE™ 0.002% (20 mcg/mL) cenegeamin-bk bj ophthalmic solution in Stage 1 NK patients who enrolled in the DEFENDO Study.

3.3.1 Alternative Treatments

The only FDA approved product for treatment of NK is OXERVATE™ 0.002% (20 mcg/mL) cenegeamin-bk bj ophthalmic solution. Alternative non-surgical treatment options may include therapeutic soft contact lenses, suture-less amniotic membrane, or tarsorrhaphy.

3.3.2 Description of the Study Product

No Study Product will be used.

4 OVERALL STUDY DESIGN AND INVESTIGATIONAL PLAN

4.1 STUDY OBJECTIVES

Primary Objective

The primary objectives are to evaluate the long-term safety and efficacy of OXERVATE™ 0.002% (20 mcg/mL) cenegermin-bk bj ophthalmic solution in Stage 1 NK patients who enrolled in the DEFENDO Study.

Secondary Objective

The secondary objectives are to evaluate the long-term efficacy of OXERVATE™ 0.002% (20 mcg/mL) cenegermin-bk bj ophthalmic solution in terms of Corneal Sensitivity, Schirmer I Test, Tear Film Break Up Time (TFBUT), Best Corrected Distance Visual Acuity (BCDVA), and Quality of Life at 24 months and 30 months.

CCI [REDACTED]

4.2 STUDY ADMINISTRATIVE STRUCTURE

This study will be performed at 4 study centers located in the United States. At each study center, the Principal Investigator (PI) will be responsible for ensuring that the investigation is conducted according to the signed Investigator agreement, the protocol, Good Clinical Practice (GCP) guidelines, and local regulations.

The PI at each study center will be responsible for the management of the study, which will consist of maintaining the study file and the patient records, corresponding with the Institutional Review Board (IRB)/Independent Ethics Committee (IEC), completing the case report forms (CRFs) and reporting Serious Adverse Events (SAE) (or other important Adverse Events (AE) as specified in [Section 9.4](#)) within 24 hours of initial awareness.

The PI is responsible for supervising any individual or party to whom the Investigator delegates study related duties and functions conducted at the study site. If the Investigator/Institution retains the services of any individual or party to perform study-related duties and functions, the Investigator/Institution should ensure this individual, or party is qualified to perform those study-related duties and functions and should implement procedures to ensure the integrity of the study-related duties and functions performed and any data generated.

4.3 OVERALL STUDY DESIGN

This clinical study will be a multi-center, open label, long-term follow-up study of the patients who were enrolled in the DEFENDO Study.

The DEFENDO Long-Term Follow-up Study will have follow-up with the patients at months 24-30. All patients will be evaluated in the real-world setting post the 6-month off treatment follow up of the DEFENDO Study through 30 months. Patient will be treated per standard of care as determined by the Investigator and will document topical ophthalmic medications. The original DEFENDO Study duration was a total of 34 weeks: a screening period of 2 weeks, followed by enrollment in 8 weeks of OXERVATE™ treatment and an Off-Treatment Follow-Up of 6 months.

After enrollment in the original DEFENDO Study, patients will be invited to enter the DEFENDO Long-Term Follow-up Study (**all standard of care is permitted**). Two (2) additional long-term follow-up visits will occur at 24- and 30-month post-treatment to evaluate long-term clinical outcomes.

[figure not shown]
All patients enrolled in the DEFENDO Study that are not meeting exclusion criteria and are not lost to follow-up will be eligible for the DEFENDO Long-Term Follow-up Study.

During the DEFENDO Long-Term Follow-up Study, the patients may be treated at the physician's discretion. Any concomitant treatment must be documented. If warranted for patient safety, the Investigator may elect to see the patient at an Unscheduled Visit(s) to evaluate the patient.

Corneal healing will be graded at a Central Reading Center per the Reading Center Charter.

Figure 1 Study Schematic

5 SELECTION OF STUDY POPULATION

Patients who were enrolled in the DEFENDO Study and were not lost to follow up will be enrolled to evaluate the long-term safety and efficacy of OXERVATE™ 0.002% (20 mcg/mL) cenegeamin-bk bj ophthalmic solution in Stage 1 NK patients.

5.1 INCLUSION CRITERIA

To be eligible for inclusion into this study, each patient must fulfil the following inclusion criteria:

1. Previously enrolled in the DEFENDO Study.
2. Satisfy all Informed Consent requirements.
 - The patient and/or his/her legal representative has read, signed, and dated the IRB approved Informed Consent document before any study-related procedures are performed.
3. Must have the ability and willingness to comply with study procedures.

5.2 EXCLUSION CRITERIA

Patients who meet any of the following criteria are NOT eligible for inclusion in the study.

1. Participating in another study that involves treating the study eye.
 - Participation in non-ocular studies is acceptable provided that the treatment is not considered to be confounding with the DEFENDO Long-Term Follow-up Study, in the opinion of the Investigator.

5.3 ASSIGNMENT OF PATIENT NUMBER

Each patient will maintain the study number they were assigned in the DEFENDO Study.

6 STUDY PRODUCT

6.1 DESCRIPTION OF STUDY PRODUCT

No Study Product will be administered during this study.

6.2 PRIOR AND CONCOMITANT MEDICATIONS

Patient topical medications taken between exiting the DEFENDO Study and enrolling in the DEFENDO Long-Term Follow-up Study will be documented as prior medications.

Patients may be treated according to the standard of care as determined by the Investigator. This may include commercially available OXERVATE™ 0.002% (20 mcg/mL) cenegeamin-bbj ophthalmic solution. Any treatment history will be documented (including over-the-counter drugs, systemic medications, herbal products, vitamins, and antacids) on the Concomitant Medications electronic CRF (eCRF) page. Medication entries should be specific to product name (if a combination drug product) and spelled correctly. The dose, unit, frequency, route of administration, start date, discontinuation date, and indication should also be recorded. For medications administered only one time, the frequency column may reflect "once."

7 STUDY PROCEDURE AND ASSESSMENTS

For the detailed description of all the clinical examinations listed below refer to the Manual of Procedures (MOP). See the [Schedule of Evaluations](#) in [Section 2](#) for the list of procedures by visit in the recommended order. The descriptions of the procedures to be performed at each visit are provided below. If possible, the same Investigator should perform the assessments for one patient.

7.1 STUDY VISITS AND EXAMINATIONS AND TREATMENT VISITS

7.1.1 Visit 1: 24-Month Long-Term Follow-Up

The 24-month long-term follow up is considered from the completion of 8-weeks of treatment. Site staff will conduct the following assessments in the order outlined below:

1. **Inclusion/Exclusion Criteria:** Inclusion/Exclusion criteria will be reviewed, and study eligibility will be determined.
2. **Informed Consent/Health Insurance Portability and Accountability Act (HIPAA):** Explain the purpose and nature of the study and have the patient or legally authorized representative read, sign, and date the IRB approved Informed Consent Form (ICF). Provide a photocopy of the signed document to the patient and place the original signed document in the patient's chart.
3. **Demographics, Medical and Ocular History:** These data from the DEFENDO Study will be carried forward into the current study's electronic data capture (EDC) System; thus, they do not need to be captured separately for this study.
4. **Record AE:** Record any AE since completing the DEFENDO Study in the AE eCRF. Data for AEs that have occurred since the completion of the DEFENDO Study should be obtained from retrospective chart review and / or patient interview. Additional information may be requested via medical records from all applicable healthcare providers, if necessary.
5. **Concomitant and Prior Ocular and Systemic Medications:** Record any concurrent ocular or non-ocular medications including information on all concomitant and previous medications used since completing the DEFENDO Study in the Concomitant Medications eCRF ([Section 6.2](#)). Data for topical ocular medications taken since the patient completed the DEFENDO Study should be obtained from retrospective chart review and / or patient interview. Additional information may be requested via medical records from all applicable healthcare providers, if necessary.

6. **IDEEL (Impact of Dry Eye on Everyday Life):** This questionnaire will be assessed by the patient using a self-administered format. This questionnaire is designed to assess health-related quality of life in patients with visual impairments by representing the patient perspective on the impact of vision problems on functioning.
7. **EQ-5D-5L:** This self-administered questionnaire will be completed by the patient before any ophthalmic examination is performed at a given study visit. The EQ-5D is a standardized measure of health status developed by the EuroQol Group to provide a simple, generic measure of health for clinical and economic appraisal.
8. **Ophthalmic Examinations:** The following examination/procedures will be performed on BOTH EYES and in the below order. Grading scales and a detailed description of the examinations/procedures are described in the MOP:
 - a. **Best-Corrected Distance Visual Acuity (BCDVA):** Vision will be measured using an Early Treatment Diabetic Retinopathy Study (ETDRS) visual acuity chart at 4 meters (13 feet) and recorded in Logarithm of the Minimum Angle of Resolution (LogMAR). BCDVA testing should precede the administration of any eye drops to dilate or anesthetize the eye, or any examination requiring contact with the eye. If vision is corrected, the same correction should be used throughout the BCDVA testing.
 - b. **External Ocular Examination:** The motility of the extraocular muscles and the appearance and function of the eyelids will be evaluated before the instillation of any dilating or anesthetic eye drops.
 - c. **Slit-Lamp Examination (SLE):** A SLE will be used to assess eyelids, lashes, conjunctiva, cornea, lens, iris, and anterior chamber. The SLE must be performed before the instillation of any dilating or anesthetic eye drops or the fluorescein agent.
 - d. **Corneal Photo without Fluorescein:** Photos of the cornea of both eyes will be taken after the SLE and before the instillation of fluorescein agent by a slit-lamp camera using white, diffuse (homogenous) frontal illumination.
 - e. **Instill Fluorescein**
 - f. **Tear Film Break-Up Time (TFBUT)**

- g. **Corneal Photography with Fluorescein:** A corneal photo of both eyes using cobalt blue illumination will be taken to document the observed corneal findings.
- h. **Corneal Sensitivity:** Corneal Sensitivity will be measured using a Cochet Bonnet aesthesiometer before the instillation of any dilating or anesthetic eye drops. Corneal sensitivity will be assessed in one quadrant of each eye.
- i. **Schirmer Test without Anesthesia (Schirmer I)**

- C CCI [REDACTED]
- C CCI [REDACTED]

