1 STUDY SYNOPSIS

CLINICAL STUDY SYNOPSIS:	
Study Number	NGF0122
Title of Study	A long-term extension study to evaluate the safety and efficacy of OXERVATE™ 0.002% (20 mcg/mL) cenegegermin-bk bj ophthalmic solution in patients with Stage 1 Neurotrophic Keratitis who were enrolled in the DEFENDO Study
Short Title	DEFENDO Long-Term Follow-up Study
EudraCT N°/IND	115892
Study Centers (Country)	4 US Study Centers
Development Phase	IV
Study Objectives	
Primary Objective
 
The primary objectives are to evaluate the long-term safety and efficacy (healing) of OXERVATE™ 0.002% (20 mcg/mL) cenegegermin-bk bj ophthalmic solution in Stage 1 Neurotrophic Keratitis (NK) patients who enrolled in the DEFENDO Study.
 
Secondary Objective
 
The secondary objectives are to evaluate the long-term efficacy of OXERVATE™ 0.002% (20 mcg/mL) cenegegermin-bk bj ophthalmic solution in terms of Corneal Sensitivity, Schirmer I Test, Tear Film Break Up Time (TFBUT), Best Corrected Distance Visual Acuity (BCDVA), and Quality of Life at 24 and 30 months.

	
CC1 [REDACTED]

Design and Methodology	
This clinical study will be a multi-center, open label, long-term follow-up study of the patients who were enrolled in the DEFENDO Study who had Stage 1 Neurotrophic Keratitis (NK) who were treated with OXERVATE™ 0.002% (20 mcg/mL) cenergermin-bk bj ophthalmic solution.
 
The DEFENDO Long-Term Follow-up Study will have follow-up with the patients at month 24 and 30 post-treatment in the DEFENDO Study: All patients will be evaluated in a real-world setting post the enrollment in the DEFENDO Study through 30 months. Patients will be treated per standard of care as determined by the Investigator CC [REDACTED]
 
The original DEFENDO Study duration was for a total of 34 weeks: a screening period of 2 weeks, followed by enrollment in 8 weeks of OXERVATE™ treatment and an Off-Treatment Follow-Up of 6 months.
 
 • After completing enrollment in the original DEFENDO Study, patients will be invited to enter the DEFENDO Long-Term Follow-up Study (all standard of care is permitted). Two (2) additional long-term follow-up visits will occur at 24- and 30-months to evaluate long-term clinical outcomes.

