7.1.2 Visit 2: 30-Month Long-Term Follow-Up

The 30-month long-term follow up is considered from the completion of 8-weeks of treatment.

1. **Record AE**
2. **Concomitant and Prior Ocular and Systemic Medications:** The Investigator will conduct a retrospective chart review and patient interview to review all medications since the previous visit.
3. **IDEEL**
4. **EQ-5D-5L**
5. **Ophthalmic Examinations:**
 - a. **BCDVA**
 - b. **External Ocular Examination**
 - c. **SLE**
 - d. **Corneal Photo without Fluorescein**
 - e. **Instill Fluorescein**
 - f. **TFBUT**
 - g. **Corneal Photography with Fluorescein**
 - h. **Corneal Sensitivity**
 - i. **Schirmer Test without Anesthesia (Schirmer I)** CCI [REDACTED]
CCI [REDACTED]

C CCI
C CCI

[REDACTED]

6. Patient Discharged from Study

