9.2 MONITORING FOR ADVERSE EVENTS

At each Follow Up visit, after the patient has had the opportunity to spontaneously mention any problems, the Investigator or appropriate designee should inquire about AEs by asking the standard questions:

- “Have you had any health problems since your last study visit?”
- “Have there been any changes in the medicines you take since your last study visit?”

AEs should be reported for any clinically relevant change in concomitant condition(s) that is the result of an untoward (unfavorable and unintended) change in a patient’s medical health. Anticipated day-to-day fluctuations of preexisting conditions that do not represent a clinically significant exacerbation or worsening need not be reported as AEs. Changes in any protocol-specific [ocular or] systemic parameter evaluated during the study are to be reviewed by the Investigator. In addition, the patient’s responses to any questionnaire utilized during the study are to be reviewed by the Investigator. Any untoward (unfavorable and unintended) change in a protocol-specific parameter or questionnaire response that is clinically relevant is to be reported as an AE. These clinically relevant changes will be reported regardless of causality.

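### Visit 1 lets adverse events over a look-back of about 18–21 months be collected by interview alone, so the descriptive AE percentages may be under-counted

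*Protocol*

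**What the plan says.** Long-term safety and healing are joint primary objectives (Protocol synopsis; SAP 1.1). The safety endpoints are AEs, slit-lamp findings and external ocular findings (Protocol 8.1.3).

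The rules on data sources are:

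- **AEs, Visit 1 (Protocol 7.1.1 item 4).** Data since "completion of the DEFENDO Study should be obtained from retrospective chart review and / or patient interview". The item adds: "Additional information may be requested via medical records from all applicable healthcare providers, if necessary".
- **Topical medications, Visit 1 (7.1.1 item 5).** "Data for topical ocular medications taken since the patient completed the DEFENDO Study should be obtained from retrospective chart review", followed by the same alternative of patient interview.
- **AEs, Visit 2 (7.1.2 item 1).** A bare heading; no source is named.
- **Medications, Visit 2 (7.1.2 item 2).** "The Investigator will conduct a retrospective chart review and patient interview to review all medications since the previous visit".
- **Any follow-up visit (9.2).** After the patient has had a chance to speak, "the Investigator or appropriate designee should inquire about AEs by asking the standard questions". The questions concern health problems and changes in medicines since the last study visit. Charts are not mentioned.

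On timing, 7.1.1 states: "The 24-month long-term follow up is considered from the completion of 8-weeks of treatment". Protocol 4.3 says that the parent study ended with "an Off-Treatment Follow-Up of 6 months". SAP 6.1 reports the number and percentage of subjects with at least one event, and plans no summary by source of the AE.

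**The concern.** Section 9.2 already expects an interview at every visit. The alternative in 7.1.1 item 4 therefore works in one direction: it makes the chart review optional. Each of the four centers can decide for itself whether to look beyond what the patient remembers.

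This matters because of what AEs do in this study. The two eye examinations show the state of the eye on the visit day. An event that began and resolved between the end of DEFENDO and Visit 1 reaches the database only if it is recalled or found in a record. Omissions lower the AE percentages, and nothing in the SAP would reveal this.

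Charts also supply dates. Under SAP 2.10, an AE with no start date is set to the first dose in the parent study, unless its stop date shows that it ended before that dose. The imputed start then falls before the extended follow-up. The SAP does not say how such an event enters the extended follow-up tables.

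**Working it through.** The documents state no look-back length and no capture rate, so there is no figure of the plan's own to reproduce.

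**1. Look-back at Visit 1**

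Inputs: Visit 1 window 24–27 months (Protocol Table 2); origin at the end of the 8-week treatment (7.1.1); parent study ends 6 months after treatment (4.3).

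Look-back = visit time − end of DEFENDO

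- Earliest: 24 − 6 = 18 months
- Latest: 27 − 6 = 21 months

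The parent study's total of 34 weeks leaves 34 − 2 − 8 = 24 weeks for the off-treatment period. At 4.348 weeks per month that is 5.5 months, and the look-back becomes 18.5–21.5 months.

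**2. Sensitivity to the time origin**

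| Reading | Source | Look-back |
|---|---|---|
| From end of treatment | Protocol 7.1.1, Table 2 | 18–21 months |
| From completion of DEFENDO | Protocol 3 and 3.2, with the Table 2 window | 24–27 months |
| Nominal weeks, 96 − 32 = 64 | SAP 2.2 | 64 / 4.348 = 14.7 months |

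Eligibility requires enrollment in DEFENDO, not completion (Protocol 5.1). For a patient who left early the period is longer. In the limiting case of exit at the first dose (an assumption), it is 24 + 8/4.348 = 25.8 to 27 + 8/4.348 = 28.8 months.

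**3. Comparison with Visit 2**

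Shortest interval since Visit 1: 30 − 27 = 3 months. Longest: 33 − 24 = 9 months. Nominal: 6 months. The two-source rule thus applies to the shorter interval, and to medications only. Nominally the Visit 1 look-back makes up 18 / (30 − 6) = 75% of the time from the end of DEFENDO to Visit 2.

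**4. Why no size can be given**

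Suppose that each event is found with probability *s*, that an affected patient has *k* events found independently of each other, and that the true share of affected patients is *p*. The SAP counts patients, so

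reported share = *p* × [1 − (1 − *s*)^*k*]

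With *p* = 30% and *s* = 0.5 to 0.8 (all assumed):

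- *k* = 1: 30% × 0.50 = 15.0% to 30% × 0.80 = 24.0%
- *k* = 2: 30% × 0.75 = 22.5% to 30% × 0.96 = 28.8%

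The result depends as much on *k* as on *s*, and the documents give neither. The gain from adding charts is equally open. If the sources are independent, joint capture is 1 − (1 − s₁)(1 − s₂): 0.85 for (0.5, 0.7) and 0.96 for (0.8, 0.8). If they overlap fully, the two together find no more than the better one alone. What can be said is that, with at most 37 patients, each affected patient missed altogether lowers a percentage by 1/37 = 2.7 points or more.

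**The case against.** Several parts of the case against stand.

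- **AEs are not singled out.** A reader might infer that AEs have a weaker rule than any other data. They do not. Topical medications at Visit 1 have the same optional wording over the same look-back, and item 5 names no source for systemic medications. The contrast is between Visit 1 and the medication item at Visit 2.
- **Visit 2 is not clearly a second gap.** Most items in 7.1.2 are bare headings whose content is given in 7.1.1. The natural reading is that the Visit 1 AE description carries over. That keeps the optional wording but adds no new omission.
- **The safety result does not rest on memory alone.** Slit-lamp and external examinations do not depend on recall. Section 9.2 also asks the investigator to review study parameters and questionnaire responses for reportable AEs. Records from other providers may be requested, and monitors will review medical records (13.1).
- **No planned comparison is biased.** The study is single-arm and exploratory, without a powered sample size, and the protocol has AEs summarized overall. Differences between centers in source use would not distort any planned contrast.

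These points limit the consequence but leave the rule unchanged. Requests for outside records are discretionary. Reviewing study parameters at the visit does not find an event that has resolved. The monitoring plan and Manual of Procedures were not available; Protocol 7 refers to the Manual for clinical examinations, not for AE sources. An exploratory, descriptive study still reports AE percentages towards a primary objective.

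**Conclusion.** The point holds for the AE part of the primary safety objective. At Visit 1, interview alone satisfies the protocol over about 18–21 months for patients who completed DEFENDO, counting from the end of treatment, and over about 15–27 months under the other time origins. On every reading the period is long, and no other safety endpoint covers it. The descriptive AE percentages may therefore be too low.

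The amount cannot be quantified from the documents. A reader might be tempted to multiply an assumed capture rate by an incidence, for example to turn 30% into 15–24%. That holds only if every affected patient has exactly one event, because the SAP counts subjects and not events. Nor do the documents show that any center will in fact skip the charts; they show only that it may. This is a permissive rule worth tightening because the remedy is cheap, not a flaw that invalidates the safety evaluation.

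**What to change.** In Protocol 7.1.1 item 4, require both retrospective chart review and patient interview for AEs since DEFENDO. In 7.1.2 item 1, state the same for the period since the previous visit, so that nothing depends on carrying over the Visit 1 text.

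The cost is a short amendment and site time to review at most 37 charts over the full Visit 1 look-back. The chart review already required at Visit 2 does not cover this, because it is for medications and reaches back only to Visit 1. Since the review is retrospective, charts of patients who have already had Visit 1 can still be reviewed before database lock. No sample size, significance level or analysis method changes.

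Optionally, add an eCRF field for the source of each AE (chart, interview or both), so that the contribution of each source can be described.
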